**Footnotes:**

\* Signs of hepatic injury are defined as

- ALT and/or AST ≥8 fold ULN
- ALT and/or AST ≥3 fold ULN and total bilirubin ≥2 fold ULN
- ALT and/or AST ≥3 fold ULN and unexplained INR >1,5
- ALT and/or AST ≥3 fold ULN and unexplained eosinophilia (>5%)
- ALT and/or AST ≥3 fold ULN and appearance of fatigue, nausea, vomiting, right upper abdominal quadrant pain or tenderness, fever and/or rash

 Investigator to confirm in writing that continuation is justified (e.g. intermittent fluctuation of transaminases).

 According to visit schedule. Consider additional control visits as adequate.

 To be decided by investigator, based on individual risk assessment.

 Close observation: Re-test ALT and AST, alkaline phosphatase, total bilirubin, and eosinophils within 48 to 72 hours, then approximately 7 days, then approximately 2 weeks by using intermediate visit lab kit.

 If clear evidence for alternative cause for hepatic injury was identified and resolved (i.e. relation to trial medication excluded, hepatic injury confirmed to have alternative explanation [other than use of IMP]): return to trial medication would be possible, after consultation with the sponsor. Prior to restart, liver laboratory values must be normal. Monitor weekly for first 4 weeks of re-introduction and every 2 weeks for the following 8 weeks.

Initial assessment and blood sampling for liver enzyme elevation follow up should be performed at the investigational site. Blood samples for additional monitoring may be collected at the investigational site, primary care physician or external laboratory with specific trial lab kits and sent to the central laboratory for analysis.

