##### **4.2.2.2 Cautionary Notes**

As nintedanib is a substrate of P-gp and, to a minor extent, CYP3A4, concomitant use of P-gp and CYP3A4 inhibitors (e.g. erythromycin) with nintedanib may increase exposure to nintedanib. Patients taking potent P-gp inhibitors (e.g. ketoconazole, erythromycin or ciclosporine) should be monitored closely for tolerability of nintedanib.

Concomitant use of P-gp and CYP3A4 inducers (e.g. carbamazepine, phenytoin, and St. John's wort) with nintedanib may decrease exposure to nintedanib. For patients taking potent P-gp inducers, selection of alternative treatment with no or minimal P-gp induction should be considered.

As the most common side effects known for nintedanib are GI effects, the concomitant use of medication with an overlapping safety profile (e.g. mycophenolate mofetil/ sodium) should be carefully considered.

Nintedanib is also associated with increases in liver enzymes and bilirubin. If in addition to the trial medication, a treatment is introduced that is known to induce AST/ALT elevations (e.g. methotrexate, bosentan), adequate measures should be taken to ensure patients safety: perform additional measurement of liver enzymes (ALT and AST, alkaline phosphatase, total bilirubin, and eosinophils) every 2 weeks for approximately 6 weeks, by using intermediated (a-visit) trial lab kit.

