The laboratory tests at intermediate ‘a’ visits will include:

Table 5.2.3: 2 Laboratory tests at intermediate ‘a’ visits

Category	Laboratory test
Biochemistry	Total protein, creatinine, electrolytes and liver function (AST, ALT, GGT, alkaline phosphatase, and total bilirubin)
Urinalysis	pH, glucose, erythrocytes, leukocytes, protein, nitrite (semiquantitative measurements; -, +, ++, +++)
Local Urine dipstick pregnancy test in all women of childbearing potential. If urine test is not acceptable to local authorities, a blood test must be done at a local laboratory.	

Overall about 110 mL blood will be taken for standard safety laboratory during the first year and about 45 mL blood will be taken any other year.

If laboratory values indicate abnormality, adequate and more frequent blood sampling may be performed at the discretion of the investigator.

In case of liver function value elevations, close monitoring must be ensured by the investigator. Refer to [Section 4.2.1.2](#) for monitoring elevations and [Section 3.3.4](#) for withdrawal criteria.

Laboratory analysis will be done using central laboratory services.

Creatinine clearance will be calculated based on serum creatinine according to Cockcroft and Gault ([R96-0690](#), [Appendix 10.2](#)).

Venous whole blood will be collected in appropriate syringes provided by the sponsor through the assigned central laboratory. Details regarding centrifuge, processing, storage and shipment of samples will be determined by the central laboratory in accordance with the sponsor. The investigators will be informed and instructed by the central lab and detailed documentation will be included in the ISF.

[figure not shown]

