#### Hepatic injury

In this trial protocol, signs of hepatic injury are defined as:

- ALT and/or AST  $\geq 8$  fold ULN
- ALT and/or AST  $\geq 3$  fold ULN and total bilirubin  $\geq 2$  fold ULN\*

- ALT and/or AST  $\geq 3$  fold ULN and unexplained INR  $> 1,5^*$
- ALT and/or AST  $\geq 3$  fold ULN and unexplained eosinophilia ( $>5\%$ )\*
- ALT and/or AST  $\geq 3$  fold ULN and appearance of fatigue, nausea, vomiting, right upper abdominal quadrant pain or tenderness, fever and/or rash

\* in the same blood draw sample.

These lab findings constitute a hepatic injury alert and the patients showing these lab abnormalities need to immediately stop the trial medication and need to be followed up according to the “drug-induced liver injury (DILI) checklist” provided in the ISF.

In case of clinical symptoms of hepatic injury (icterus, unexplained encephalopathy, unexplained coagulopathy, right upper quadrant abdominal pain, etc.) without lab results (ALT, AST and total bilirubin) available, the investigator should make sure these parameters are analysed, if necessary in an unscheduled blood test. Should the results meet the criteria of hepatic injury alert, the procedures described in the DILI checklist should be followed.

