## 8.7 ADMINISTRATIVE STRUCTURE OF THE TRIAL

The trial is sponsored by Boehringer Ingelheim (BI).

The Coordinating Investigator is responsible to coordinate Investigators at the different centres participating in this multicentre trial. Tasks and responsibilities are defined in a contract.

Relevant documentation on the participating (Principal) Investigators and other important participants, including their curricula vitae, will be filed in ISF. The investigators will have

access to the BI clinical trial portal (Clinergize) to facilitate document exchange and maintain electronic ISF.

Boehringer Ingelheim has appointed a Trial Clinical Monitor, responsible for coordinating all required activities, in order to manage the trial in accordance with applicable regulations and internal SOPs, direct the clinical trial team in the preparation, conduct, and reporting of the trial, ensure appropriate training and information of local clinical monitors (CML), Clinical Research Associates (CRAs), and Investigators of participating countries.

The organisation of the trial in the participating countries will be performed by the respective local or regional BI-organisation (Operating Unit, OPU) in accordance with applicable regulations and internal SOPs, or by a Contract Research Organisation (CRO) with which the responsibilities and tasks will have been agreed and a written contract filed before initiation of the clinical trial.

Tasks and functions assigned in order to organise, manage, and evaluate the trial are defined according to BI SOPs.”

Data Management and Statistical Evaluation will be done by BI according to BI SOPs.

A list of responsible persons and relevant local information can be found in the ISF.

Central laboratory facilities will handle all laboratory analyses of the trial. Samples for intermediate measurements (liver enzymes, creatinine) and pregnancy tests may be collected at a local doctor by using trial specific lab kits that will be sent to central laboratory for analyses.

  
Interactive Response technology (IRT) vendor will be used in this trial.

Details will be provided in IRT Manual, the Spirometry Manual and Central Laboratory Manual, available in the ISF.

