## 10.3 VISIT MODIFICATION IN EXCEPTIONAL CIRCUMSTANCES

INITIAL	MODIFIED or ADDED
Face-to-face patient visit performed by a physician/under the responsibility of a physician on site.	Remote or home visit performed by the investigational site physician/under the responsibility of the investigational site physician to ensure the wellbeing of a patient and to collect at least: Adverse Events / Concomitant Treatments and Drug Interruption
Regular on site safety lab test using central lab kits: 
 
• Haematology, Biochemistry, Electrolytes, Coagulation, Urinalysis every 16 weeks using central lab; Liver enzyme monitoring every 8 weeks, using central lab
 
• Pregnancy test every 4-6 weeks (possible at home)
 
	
 
• Under treatment with nintedanib, regular liver enzyme monitoring is required and needs to be ensured by the investigational site, but can be done at a local lab / local doctor. The investigator has to ensure medical review and proper documentation in the eCRF. Minimum required safety lab parameters are AST, ALT, GGT, ALK and total bilirubin.
 
• Urine pregnancy tests (for women of childbearing potential only) are regularly required and may be done at local lab / local doctor, or at home.
 
• Decision whether to continue nintedanib treatment should be made based on an individual risk assessment for that individual patient and weigh up the benefits of an extended lab interval to maximum 16 weeks versus an interruption of treatment.
 
• Medical decision has to be documented in patient's source notes.
 
 If remote patient visits and/or local liver enzyme monitoring cannot be performed, nintedanib treatment needs to be interrupted.
If liver function tests are out of the range, the per protocol rules apply => dose reduction	If the patient cannot come to site for receiving new dose treatment and/ or patient safety and follow up safety lab testing cannot be guaranteed, treatment needs to be interrupted.
Dispensation of study treatment on site	
 
• Site / Depot to patient IMP shipments
 
• Patients must consent to providing contact details for shipping purposes
 
• Patients should retain all unused IMP and packaging, and return it when they are able to return to the site.
 

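### INR is required neither in the a-visit panel nor in the close-observation re-tests, so the same-sample INR criterion for hepatic injury can go unassessed in interrupted patients

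*Protocol*

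**What the plan says.** Protocol 5.2.11.1 lists five signs of hepatic injury: ALT/AST ≥8×ULN, or ALT/AST ≥3×ULN with bilirubin ≥2×ULN, with unexplained INR >1.5, with unexplained eosinophils >5%, or with symptoms. The three laboratory combinations must be found "in the same blood draw sample". SAP 5.4.4 repeats the same-sample rule, and deviation C3a in SAP Table 6.2:1 uses that definition. Protocol 3.3.4.1 makes these signs a reason for permanent discontinuation.

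Full visits measure INR and a white-cell differential (Table 5.2.3:1). The a-visit biochemistry is "Total protein, creatinine, electrolytes and liver function (AST, ALT, GGT, alkaline phosphatase, and total bilirubin"; the other rows of Table 5.2.3:2 are urinalysis and a pregnancy test. Section 8.7 describes the same samples in the same way: "Samples for intermediate measurements (liver enzymes, creatinine) and pregnancy tests may be collected at a local doctor by using trial specific lab kits". Appendix 10.3 summarises the regular schedule as "Haematology, Biochemistry, Electrolytes, Coagulation, Urinalysis every 16 weeks using central lab; Liver enzyme monitoring every 8 weeks, using central lab".

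When ALT/AST rises, footnote 4 to Table 4.2.1.2:1 prescribes: "Close observation: Re-test ALT and AST, alkaline phosphatase, total bilirubin, and eosinophils within 48 to 72 hours", then again at about 7 days and about 2 weeks, with the intermediate-visit kit. Section 4.2.2.2 orders the same analytes after a new hepatotoxic co-medication, "by using intermediated (a-visit) trial lab kit". Neither list names INR. In exceptional circumstances Appendix 10.3 sets a floor: "Minimum required safety lab parameters are AST, ALT, GGT, ALK and total bilirubin".

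**The concern.** In the 3 to <5× and 5 to <8×ULN columns of Table 4.2.1.2:1, management depends on there being no signs of hepatic injury. One of the five signs needs an INR from the same sample as the raised ALT/AST. If the elevation first appears at an a-visit, the plan requires no such INR before the decision at two weeks. A patient whose only positive sign would have been INR is handled as having none and, once ALT/AST falls below 3×ULN, may be restarted.

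In the analysis, the visible SAP text does not say how an unmeasured INR enters the proportion with signs of hepatic injury. The general rule in SAP 7 uses all patients as denominator unless otherwise specified. A reader of the table could not tell a criterion that was negative from one that was never tested.

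**Working it through.** The plan states no figure on this point, so the check sets its lists side by side and counts draws and days.

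**1. Which criteria each listed draw can assess**

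| Criterion | Full visit | a-visit | Footnote 4 re-test | Appendix 10.3 minimum |
|---|---|---|---|---|
| ALT/AST ≥8× | yes | yes | yes | yes |
| ≥3× and bilirubin ≥2× | yes | yes | yes | yes |
| ≥3× and INR >1.5 | yes | no | no | no |
| ≥3× and eosinophils >5% | yes | not listed | ordered | no |
| ≥3× and symptoms | yes | yes | yes | yes |

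INR is the firm gap. Eosinophils are an inconsistency: footnote 4 and Section 4.2.2.2 order them from the intermediate kit, but Table 5.2.3:2 lists no differential for it.

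**2. Draws up to the decision.** One a-visit draw plus three re-tests (48–72 hours, about 7 days, about 2 weeks): 1 + 3 = 4 draws, none with INR required.

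**3. Chance help from a full visit.** Planned days from the Flowchart:

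- V2a to V3: 29 − 15 = 14 days
- V3a to V4: 85 − 57 = 28 days
- V4a to V5: 169 − 127 = 42 days
- V5a to V6: 253 − 211 = 42 days
- V6a to V7: 365 − 309 = 56 days
- afterwards, week 60 to 68 and so on: 8 × 7 = 56 days

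A full visit falls within 14 days after 1 of 5 a-visits in year 1, and after 1 of 11 to week 148. Even that one is not assured: with ±3 days at both V2a and V3, the gap is 14 ± 6, or 8 to 20 days. Within the 4-week limit for drug-related interruption (Table 4.2.1:1), the counts are 2 of 5 and 2 of 11.

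**4. What happens to the patient (ALT/AST 3 to <8×ULN at an a-visit, no other sign positive)**

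- *Dose reduced at once* (possible at 3 to <5× on 150 mg bid). Section 6.2.4 requires a visit with a safety laboratory. If that means Table 5.2.3:1, INR is drawn, probably while ALT/AST is still raised.
- *Interrupted, then <3×ULN, previously on 150 mg bid.* Restart at 100 mg bid is a dose reduction, so Section 6.2.4 should apply. INR is then measured, but with ALT/AST <3×ULN the same-sample criterion can no longer be met.
- *Interrupted, then <3×ULN, already on 100 mg bid.* Restart is at the same dose. Section 6.2.4 covers reductions and increases only, so the patient may restart with no INR at all.
- *Still ≥3×ULN at two weeks.* The drug is stopped whatever the INR, and the EOT visit carries a safety laboratory (Flowchart).

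**5. Share of scheduled tests.** Post-baseline a-visits are 5 of 10 liver tests to week 52, 11 of 22 to week 148 and 20 of 39 to week 286 (5.5 years); with EOT added, 5 of 11, 11 of 23 and 20 of 40.

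**The case against.** The best defence is that enzyme-first screening with a wider panel only when needed is reasonable, and that the plan has several routes to an INR. Taking these in turn:

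- *DILI checklist.* It is not among the documents. Sections 5.2.3 and 5.2.11.1 invoke it once the hepatic-injury criteria are fulfilled, so it cannot supply the test needed to fulfil them.
- *Investigator discretion.* Section 5.2.3 permits extra sampling but does not name INR or require it.
- *Safety laboratory at restart, and at EOT.* This stands in large part. Most re-exposure from 150 mg bid should be preceded or accompanied by an INR, and persistent elevation ends treatment with a further laboratory. What remains is the formal criterion in interrupted patients and restart in those already on 100 mg bid.
- *Rarity.* This also stands. The patient must have ALT/AST 3 to <8×ULN, bilirubin <2×ULN, no eosinophilia, no symptoms and an unexplained INR >1.5, and full-dose anticoagulation is excluded at entry.
- *Eosinophils.* A reader might infer from Table 5.2.3:2 that they too go unassessed. Footnote 4 orders them in the same re-tests as ALT/AST, so the text supports only a mismatch between table and footnote.
- *Half of all liver tests.* A reader might infer that hepatic injury cannot be assessed at half the scheduled tests. That share counts visits, not patients with elevations, and at least three of the five criteria remain assessable at every a-visit.
- *Appendix 10.3.* Its panel is a minimum for exceptional circumstances, and treatment must be interrupted where follow-up testing cannot be assured. It widens the gap only in those circumstances.

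**Conclusion.** The point holds, at minor severity. When ALT/AST ≥3×ULN is first found at an a-visit, no draw up to the two-week decision is required to assess the INR criterion, unless the dose is reduced at once or a full visit happens to fall in that time. The patients concerned are interrupted, have ALT/AST 3 to <8×ULN and have no other positive criterion. The documents give no basis for estimating their number.

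Two stronger conclusions are tempting and not supported. One is that patients are generally re-exposed without any INR: restart from 150 mg at 100 mg bid should trigger the Section 6.2.4 laboratory. The other is that the trial's safety results are compromised. The primary endpoint is the incidence of adverse events, the table of adverse events of special interest is investigator-reported (SAP 7.8.1.1), and deviation C3 is a manual review that excludes nobody. Only the hepatic-injury proportion in SAP 5.4.4 and deviation C3a share the blind spot. That an unmeasured INR would be counted as negative is a possibility, not something the SAP states.

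The conclusion assumes that the kit holds what Table 5.2.3:2 lists (the Laboratory Manual is not available), that the Section 6.2.4 safety laboratory is the full panel of Table 5.2.3:1 (the section does not say), and that visits fall on their planned days.

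**What to change.** Protocol:

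1. Add INR to the re-test list in footnote 4 to Table 4.2.1.2:1.
2. For any ALT/AST ≥3×ULN, including one found at a local laboratory under Appendix 10.3, require INR and eosinophils in the same draw as ALT/AST, at least at the 48–72 hour re-test.
3. Make the listed contents of the re-test kit match, which also removes the eosinophil inconsistency.

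INR should not be added to routine a-visits or to Section 4.2.2.2 draws with ALT/AST <3×ULN: the criterion cannot apply there, and a-visit samples may be taken off site.

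SAP 5.4.4 (optional): keep the definition, and report the number of patients with ALT/AST ≥3×ULN and no positive criterion for whom INR was never measured in the same sample. The table of adverse events of special interest stays as it is.

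Cost: one small coagulation tube and its handling per re-test, in patients with elevations only. Assuming 2–5 mL per re-test, this is 2–5 mL if done only at 48–72 hours and 3 × 2–5 = 6–15 mL over all three, against the planned 110 mL in the first year and 45 mL in any other. Re-tests taken off site are harder to handle, but the protocol already says "Initial assessment and blood sampling for liver enzyme elevation follow up should be performed at the investigational site", so the 48–72 hour draw is feasible. The SAP change is one extra count.

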#### 5.2.4 Electrocardiogram

The 12-lead ECGs will be recorded as scheduled in the [Flowchart](#). The investigator or a designee will evaluate whether the ECG is normal or abnormal and whether it is clinically relevant, if abnormal. ECGs may be repeated for quality reasons and the repeated recording used for analysis.

Additional ECGs may be recorded for safety reasons. Dated and signed printouts of ECG with findings should be documented in patient’s medical record.

Clinically relevant abnormal findings will be reported either as baseline condition (if identified at the screening visit) or otherwise as adverse events and will be followed up and/or treated as medically appropriate.

#### **5.2.10 Other safety parameters**

Worsening or new onset of SSc organ involvement (e.g. renal, cardiac, GI, vasculopathy) will be assessed via evaluation of adverse events / serious adverse events.

## 5.2.11 Assessment of adverse events

### 5.2.11.1 Definitions of AEs

#### Adverse event

An adverse event (AE) is defined as any untoward medical occurrence in a patient or clinical investigation subject administered a medicinal product and which does not necessarily have to have a causal relationship with this treatment.

An AE can therefore be any unfavourable and unintended sign (including an abnormal laboratory finding), symptom, or disease temporally associated with the use of a medicinal product, whether or not considered related to the medicinal product.

#### Adverse reaction

An adverse reaction is defined as a response to a medicinal product which is noxious and unintended. Response in this context means that a causal relationship between a medicinal product and an adverse event is at least a reasonable possibility. Adverse reactions may arise from use of the product within or outside the terms of the marketing authorisation or from occupational exposure. Conditions of use outside the marketing authorization include off-label use, overdose, misuse, abuse and medication errors.

#### Serious adverse event

A serious adverse event (SAE) is defined as any AE which fulfils at least one of the following criteria:

- results in death,
  - is life-threatening, this refers to an event in which the patient was at risk of death at the time of the event; it does not refer to an event that hypothetically might have caused death if more severe.
  - requires inpatient hospitalisation or
  - prolongation of existing hospitalisation,
  - results in persistent or significant disability or incapacity, or
  - is a congenital anomaly / birth defect,
- or
- is to be deemed serious for any other reason if it is an important medical event when based upon appropriate medical judgment which may jeopardise the patient and may require medical or surgical intervention to prevent one of the other outcomes listed in the above definitions.

Examples of such events are intensive treatment in an emergency room or at home for allergic bronchospasm, blood dyscrasias or convulsions that do not result in hospitalisation or development of dependency or abuse.

For Japan only: the following events will be handled as “deemed serious for any other reason”. AEs which possibly lead to disability will be reported as SAEs.

### **AEs considered “Always Serious”**

Every new occurrence of cancer of new histology must be classified as a serious event regardless of the duration between discontinuation of the trial medication and must be reported as described in section [5.2.11](#), subsections “AE Collection” and AE reporting to sponsor and timelines”.

Cancers of new histology and exacerbations of existing cancer must be classified as a serious event regardless of the duration between discontinuation of the drug and must be reported as described in section [5.2.11](#), subsections “AE Collection” and AE reporting to sponsor and timelines”

In accordance with the European Medicines Agency initiative on Important Medical Events, Boehringer Ingelheim has set up a list of further AEs, which by their nature, can always be considered to be “serious” even though they may not have met the criteria of an SAE as defined above.

The latest list of “Always Serious AEs” can be found in the eDC system. A copy of the latest list of “Always Serious AEs” will be provided upon request. These events should always be reported as SAEs as described above.

